## **2. Adequacy of Protection Against Risks**

### **a. Informed Consent and Assent**

An initial screening and consent meeting will be scheduled with the PI over e-mail and will take place in person at the research lab. The potential participant will be sent a copy of the consent form to review in advance (at least 48 hours before the meeting). The details of the study & potential risks will be discussed in this meeting. The potential participant will have an opportunity to ask any questions, and will additionally be screened for participation (inclusion/exclusion criteria). If the person qualifies and agrees to participate after written and oral information are provided on the study, they will be given the opportunity to sign the informed consent document and enrolled in the study. They will also be informed that they can choose to withdraw at any time.

### **b. Protections Against Risk**

**Physical risks:** All portions of research, including exercise and heating sessions, will be closely supervised by study staff. We have procedures and criteria in place to discontinue exercise or heating in the event of unusual heart rate or blood pressure responses, difficulty breathing, chest pain, elevated temperature, or any symptoms related to heat illness. We will also monitor subjective ratings every 5 minutes to assess physical comfort. During leg heating, water temperature will be continuously monitored and set at a level (42°C) well below the threshold for burning (47°C). Ice and fans will be on hand to initiate rapid cooling if needed.

Breach of confidentiality: All research activity including subject screening and data collection will be performed and stored at Providence College. Subject names, contact information, health history, and other information that can be traced back to the subject will be kept securely and separately from data collected for the study. Personal information will be kept in a locked office and away from data. Collected data will have the subject's identification code and some computer software used to collect data (LabChart) will have the date and time marked on the file. Protocol sheets used during data collection will only have the subject's ID. The tests will have a subject ID and may contain other pertinent information needed to clinically evaluate the test, such as age, gender, and blood pressure measurement. All data will be stored in a secure server and encrypted hard drives. All key personnel have completed education on the use of human subjects (CITI, Good Clinical Practices [GCP] training) in compliance with NIH regulations.

Medical emergencies: In the unlikely event of a medical emergency or adverse response, the Health Sciences Laboratory Medical Emergency Safety Plan will be followed. Adverse events will be handled by immediately stopping any testing and monitoring the subject (including signs, symptoms, and blood pressure) as necessary, with immediate medical assistance available through Providence College emergency procedures if necessary.

Incidental Findings: The cardiovascular assessments we make as part of this research will provide insight into the health of the participant. In the event that an individual has a result (very high blood pressure, abnormal ECG), no diagnosis will be made by study staff. However, the results will be shared with the participant and we will suggest they follow up with their primary care provider.

### **3. Potential Benefits of the Proposed Research to Research Participants and Others**

There are no direct benefits from participating in this study. The interventions in this study (moderate exercise, heat exposure) have been shown to improve blood pressure and cardiovascular health with repeated use, but it is unlikely that a meaningful long-term change in fitness or health will occur with this acute protocol.

More broadly, the results of this study have important health implications in the treatment of hypertension using lifestyle interventions. The findings have the potential to improve non-pharmacological treatment of hypertension by developing an exercise and heat exposure protocol that substantially reduces blood pressure and improves cardiovascular risk profile for the >100 million Americans with hypertension. Each individual participant will have the option to review their results from their trials after completion of the study, and may share these results with their physician to discuss lifestyle interventions to prevent hypertension. This potential benefit outweighs the minimal risks (muscle soreness, mild discomfort during study procedures) associated with the study.

### **4. Importance of the Knowledge to be Gained**

Nearly half of the U.S. population has elevated blood pressure, and 1 in 3 Americans has diagnosable hypertension. Progression to more severe disease states carries a significant health and financial burden, so low-cost, non-pharmacological interventions provide a critical avenue to prevent disease progression. The results of this work will provide insight into the possible complementary nature of exercise and heat exposure to reduce blood pressure, and the mechanistic underpinnings that may allow for a more targeted lifestyle approach to different types of hypertension (related to sympathetic overactivity, impaired blood vessel function, or both). Further, as nocturnal dipping (the decrease in blood pressure that occurs during sleep) is related to disease severity and adverse cardiovascular outcomes, the examination of overnight responses will provide insight into the efficacy of exercise, heat, or both to improve overnight

blood pressure. Given the health burden of hypertension on individual and on society, the potential benefits outweigh the risks of individuals participating in this research.

### **Statistical Design and Power**

This study investigates the potential for heat therapy to supplement or augment exercise for blood pressure reduction. To estimate expected effect sizes, we calculated standardized mean differences in our key outcomes using pilot data from our healthy participants:  $d = (x_{baseline} - x_{intervention})/S$ , where x represents the baseline (no intervention) and post-treatment (combined exercise and heat) values and S is the standard deviation. This effect size calculation reflects differences in outcome means anticipated for the proposed study. Taking into consideration the relatively low costs and low risks of hot water leg immersion, these differences are not only statistically significant, but also clinically meaningful at the individual and population levels.

**Primary analyses:** The primary outcome variable for Specific Aim 1 is mean nocturnal blood pressure. Using previous data from our lab in healthy men and women, a power analysis indicates that a minimum of 8 participants should be required to see changes between intervention and control treatments using a repeated-measures ANOVA design. For Specific Aim 2, our primary outcome variable is the time domain analysis of Heart Rate Variability (standard deviation of normal to normal R-R intervals; SDNN). Using pilot data from a study examining post-exercise hot or cold water immersion, a minimum of 10 participants is required to see differences in HRV between treatments using a repeated-measures ANOVA design. For Specific Aim 3, data from existing literature examining endothelial function (flow-mediated dilation) before and after a single bout of exercise in individuals with hypertension indicates that a minimum of 10 participants would be required to see significant differences in % dilation (the primary outcome of FMD analysis) between treatments. Given that there may be sex differences in the magnitude, timing, or mechanisms of blood pressure responses to exercise and heating, we plan to recruit sufficient numbers (10 men, 10 women) to allow for a statistical comparison between sexes. Significance for each test will be evaluated with a two-sided alpha,  $p < .05$ .

**Projected effect size:** Based on preliminary data from our pilot work, we project large within-subject effects across multiple outcomes. We used mean changes in the primary outcome variables, and estimated the standard deviation from the baseline data in our pilot participants or published values using exercise or acute heat exposure as accurate estimates. Effect sizes were calculated as mean change from baseline (control) to post-intervention as follows: Mean arterial pressure  $d = 1.33$ , SDNN (HRV)  $d = 1.03$ , FMD  $d = 1.12$ .

Results will be analyzed using a repeated measures ANOVA (each participant will complete all treatments in a randomized, counterbalanced design) with four trials (Control, Ex, ExHT, HT). Statistical significance will be set at  $\alpha=0.05$  and power at 80%. Secondary analyses using a mixed-model ANOVA design may also be used to examine possible differences in magnitude of change between men and women for each variable. Descriptive statistics will be presented including mean, median, standard deviation, and range.

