## **Human Subjects Procedures**

### **a. Human Subjects Involvement, Characteristics, and Design**

Study design: This study will examine heart rate variability (HRV), endothelial function (FMD), and overnight blood pressure in response to acute moderate aerobic exercise followed by leg heating in 42°C water (Ex + HT), aerobic exercise followed by a sham leg immersion in 33°C water (Ex), leg heating alone in 42°C water (HT), or control conditions (no exercise or heat exposure) in adults with elevated blood pressure. The study will consist of four trials, administered in a randomized, counterbalanced fashion, with all participants completing all treatments, with at least 5 days between each trial.

Subject population: The subject population will be adults with elevated blood pressure (defined as resting blood pressure >120/80 mmHg; not diagnosed hypertension). Inclusion criteria for all subjects will be age 18-50, BMI between 18-39.9, not taking any anti-hypertensive medications, no history of heat illness. Blood pressure will be measured at the screening visit and volunteers must have duplicate resting blood pressures >120/80 (taken after 15 minutes of quiet rest in the lab) in order to qualify for the study. These inclusion criteria, including age range, were selected to minimize the risk of acute cardiovascular events during exercise. All subjects must be capable of walking 30 min at a moderate intensity on a treadmill. An effort will be made to recruit men and women in equal numbers, and for the diversity of the subject pool to match the local community.

Research sites: This is a single-site study and all research activities will be conducted at Providence College.

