### **b. Study Procedures, Materials, and Potential Risks**

Volunteers will report to the lab for an introductory visit and screening 24 hours prior to their first study day. After a review of study procedures and resting blood pressure measurement, they will be instrumented with an ambulatory blood pressure cuff which will take hourly measurements for the 24 hours preceding their first study day for familiarization with the equipment.

Upon arrival for testing the following afternoon, weight and height will be assessed, and volunteers will be instrumented with a 3-lead ECG and a beat-by-beat blood pressure monitor before lying supine in a room-temperature lab for 15 minutes prior to baseline (pre-intervention) measures of heart rate, heart rate variability (HRV), blood pressure, and flow-mediated dilation (FMD) of the brachial artery (described below). After baseline measures, volunteers will complete the daily protocol, consisting of either exercise + heat (Ex + HT), exercise + sham immersion (Ex) or heat alone (HT). On the control day, only baseline measures will be taken and the volunteer will be instrumented with the ambulatory blood pressure cuff with instructions to refrain from exercise or heat exposure during the 24h measurement.

Blood Pressure measurement: Blood pressure will be measured regularly in the lab for safety monitoring using a clinical-grade automated blood pressure cuff. Ambulatory blood pressure will be measured for a 24 hour period following each of the four conditions: control (no exercise or heat), Exercise, Heat Therapy, and combined Exercise and Heat Therapy. The Welch-Allyn

ambulatory monitor inflates once per hour and stored blood pressure readings for download by the research staff.

Heart Rate Variability (HRV): HRV will be measured during supine rest on a padded exam table. Participants will be instrumented with three foam stickers on the shoulders and hip which connect to a device that records and analyses heart rhythm (Finapres Nova). They will be asked to breathe to a metronome (paced breathing) for a period of 10 minutes to ensure adequate data collection.

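### Cheap improvement, not an error: the four-trial crossover ANOVA names only trial, and no rule covers a participant who does not complete all four trials

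*Combined protocol and SAP*

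**What the plan says.** The analysis sentence in Statistical Design and Power reads: "Results will be analyzed using a repeated measures ANOVA (each participant will complete all treatments in a randomized, counterbalanced design) with four trials". It names no visit, period or sequence term. The design section describes the four trials as "administered in a randomized, counterbalanced fashion, with all participants completing all treatments, with at least 5 days between each trial", so both places presume complete data.

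Other sections allow for incomplete data. Informed Consent and Assent says: "They will also be informed that they can choose to withdraw at any time". Protections Against Risk says: "Adverse events will be handled by immediately stopping any testing and monitoring the subject". It does not say whether a stopped trial is repeated or how it is analysed. No section gives an analysis set, a missing-trial rule, a replacement rule or a dropout allowance.

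The only mixed model in the plan is optional and serves the comparison of men and women: "Secondary analyses using a mixed-model ANOVA design may also be used".

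**The concern.** Two things can cost precision.

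- **Visit effects.** If outcomes shift from visit to visit, a model with trial as its only factor puts the shift into the error term. Counterbalancing keeps the trial means unbiased but does not remove the extra noise.
- **Incomplete participants.** A classical repeated-measures ANOVA needs all four trials per person. A participant who leaves after three contributes nothing, although three trials were collected. Without a written rule, the choice to drop, replace or repeat is made after data have been seen.

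The contrast most exposed is Ex+HT against Ex. The section opens with that question: "This study investigates the potential for heat therapy to supplement or augment exercise for blood pressure reduction". The effect sizes it then gives are all against baseline (control), so no margin is stated for the contrast that isolates the added heat.

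**Working it through.** **Inputs from the plan.** Four trials, counterbalanced; 20 participants (10 men, 10 women); two-sided alpha 0.05; power 80%; d = 1.33 (mean arterial pressure), 1.03 (SDNN), 1.12 (FMD); stated minimum sizes 8, 10 and 10.

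**Assumed inputs.** The plan gives no visit effect, withdrawal rate, within-person correlation or sequence scheme. I assumed a Williams square (4 sequences of 5 people), with the within-person residual SD as the unit.

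**1. The plan's own figures.** Reading d as a standardised within-person difference, a paired t-test (noncentral t) needs 7, 10 and 9 participants (power 0.833, 0.825, 0.836). The stated 8, 10 and 10 are reproduced to within one; power at those sizes is 0.895, 0.825 and 0.882.

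**2. Cost of a visit term, complete data, no visit effect.** Residual df without the term are 3(n - 1) = 57 at n = 20, and with it 57 - 3 = 54. The critical t rises from 2.0025 to 2.0049, a ratio of 1.0012, so intervals are 0.12% wider. The same calculation gives 0.20% at n = 16 and 0.59% at n = 10. This relies on exact visit balance. With 20 distinct orders out of the 24 possible the cost is 0.56%; with unrestricted random orders it averages 2.9%.

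**3. Gain if there is a visit trend, complete data.** The ANOVA mean square error is (57 + 20 × Σ(v - v̄)²)/57, and the interval ratio (ANOVA to visit model) is √MSE × 2.0025/2.0049.

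| Linear trend, visit 1 to 4 (SD) | Σ(v - v̄)² | MSE | ANOVA interval |
|---|---|---|---|
| 0 | 0 | 1.000 | 0.1% narrower |
| 0.25 | 0.035 | 1.012 | 0.5% wider |
| 0.5 | 0.139 | 1.049 | 2.3% wider |
| 1.0 | 0.556 | 1.195 | 9.2% wider |

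**4. Gain if participants withdraw, no visit effect.** With permanent withdrawal at rate w per later visit and q = 1 - w, expected completers are 20q³ and expected trials collected are 20(1 + q + q² + q³). Variance and width ratios (complete-case ANOVA to all-trials model with visit) come from 1,500 simulations per cell, at within-person correlations of 0.3, 0.5 and 0.8.

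| w | Completers | Trials collected | Trials used | Discarded | Variance ratio | ANOVA interval wider by |
|---|---|---|---|---|---|---|
| 2.5% | 18.5 | 77.0 | 74.1 | 2.9 | 1.026-1.033 | 1.2-1.5% |
| 5% | 17.1 | 74.2 | 68.6 | 5.6 | 1.055-1.071 | 2.6-3.4% |
| 10% | 14.6 | 68.8 | 58.3 | 10.5 | 1.116-1.155 | 5.6-7.4% |

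At 10% and correlation 0.5, contrast variances are 0.1230 (mixed model) and 0.1401 (complete cases). These are worth 2/0.1230 = 16.3 and 2/0.1401 = 14.3 complete participants.

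Fixing the number of withdrawals instead (correlation 0.5, balanced sequences), 2, 4 or 6 of 20 leaving makes the mixed-model interval 1.9%, 4.3% or 7.0% narrower than the ANOVA's. Within that model the visit term costs 0.2-0.8% for 1 to 6 withdrawals. With unrestricted random orders the change is a net loss up to about 2 withdrawals.

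**5. Both together (correlation 0.5).** A 0.5 SD trend with 5% withdrawal makes the ANOVA interval 5.7% wider; a 1.0 SD trend with 10% makes it 16.7% wider.

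**6. Power.** For the smallest stated effect, the noncentrality is 1.03/√(1 - ρ)/√(2/n) on 3(n - 1) df.

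| Completers | ρ = 0 | ρ = 0.5 |
|---|---|---|
| 20 | 0.893 | 0.995 |
| 16 | 0.813 | 0.981 |
| 14 | 0.757 | 0.964 |

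For Ex+HT against Ex, taking d = 0.5 and ρ = 0.5 purely as an illustration, power is 0.59 with 20 complete. At 10% withdrawal it is about 0.50 with the mixed model and 0.45 with complete cases; at 5%, about 0.55 and 0.52.

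**7. Unequal variances.** With residual SDs of 1, 1, 1.5 and 1.5 across trials (4,000 simulations), pairwise type I error is 1.2-9.8% with one pooled error and 4.7-5.2% with each pair's own error. With 10% withdrawal the ranges are 1.5-8.7% and 4.4-5.2%. A mixed model with a single residual variance and a pooled-error ANOVA share this weakness.

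**The case against.** - **The headline cost is a best case.** This stands. The plan says counterbalanced but gives no sequence scheme, and 10 per sex does not divide by 4. The 0.1% figure needs 20 completers and exact visit balance. Unrestricted orders, where the cost is about 3%, are not the natural reading of counterbalanced.
- **The gain may be nil.** This stands. The plan reports neither a visit effect nor a dropout rate. Participants also wear the ambulatory cuff "for the 24 hours preceding their first study day for familiarization with the equipment", which lessens a first-use effect on cuff pressure. HRV and FMD are measured before the intervention on each test day; if change from same-day baseline is analysed (the plan does not say), much of a visit shift cancels.
- **Power has a cushion.** This largely stands. Twenty are recruited against minima of 8 to 10. Only near-zero within-person correlation brings power below 80% at 14 completers; a plain paired t-test at d = 1.03, read as a within-person difference, still has 0.945. Zero correlation is not excluded, because the plan takes its SD from baseline or published data.
- **A pooled-error mixed model could be worse than ordinary paired follow-ups.** This stands and shapes the fix: the plan does not say that its follow-up contrasts use a pooled error.

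A reader might infer that the planned ANOVA is biased or invalid. The documents do not support that: with balanced order and complete data its trial means are unbiased.

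**Conclusion.** The point holds as a cheap improvement in precision and prespecification. It is certain that the plan names only trial and has no rule for incomplete participants. Listwise deletion is inferred from the usual ANOVA procedure.

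The likely benefit is modest: about 1-3% in interval width at 2.5-5% withdrawal per later visit, and more only with heavier loss or a marked visit trend. All these sizes rest on assumed inputs. It matters mainly for Ex+HT against Ex, which has no stated effect size.

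Two stronger readings should be resisted. The stated effects against control are not shown to be underpowered. Nor does the model change rescue the Ex+HT against Ex contrast: in the illustration above, no analysis reaches 80%, even with all 20 complete.

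**What to change.** In Statistical Design and Power:

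1. Make the primary analysis a linear mixed model with fixed effects for trial and visit number (1-4) and a participant effect, using all available trials, with a small-sample df method such as Kenward-Roger.
2. Base pairwise contrasts on variances that may differ across trials, through an unstructured covariance or each pair's own error from participants who have both trials.
3. State the missing-at-random assumption. Report every missing trial with its reason, because a loss after an adverse event may depend on the response in that trial.
4. State the sequence scheme, since the cost of the visit term depends on it.
5. Keep the planned ANOVA as a sensitivity analysis. If the comparison of men and women is run, use the same model plus sex and sex-by-trial.

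This is wording only, with no new measurement. Besides the visit-term cost above, it needs the missing-at-random assumption and software that offers the df method. Pair-specific error has its own price if variances are in fact equal: with 20 complete, 19 df give a critical t of 2.0930 against 2.0025 on 57 df, a ratio of 1.045, so intervals are about 4.5% wider than with pooled error. Ordinary paired follow-ups to the ANOVA would pay the same.

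### SDNN and % dilation are measured before treatment on each study day, but the four-trial ANOVA names no same-day pre-treatment term and does not define the outcome, so precision among the active conditions may be lost.

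*Combined protocol and SAP*

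**What the plan says.** The section on study procedures (section b) has the participant rest supine "prior to baseline (pre-intervention) measures of heart rate, heart rate variability (HRV), blood pressure, and flow-mediated dilation (FMD) of the brachial artery", and then complete that day's protocol. The arrival is described for the first study day, but the text runs on into the daily protocol and the control day, so I read it as applying to every study day. On the control day these baseline measures are the only laboratory measures taken.

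The primary model is in Statistical Design and Power, in the paragraphs on projected effect size: "Results will be analyzed using a repeated measures ANOVA (each participant will complete all treatments in a randomized, counterbalanced design) with four trials", namely Control, Ex, ExHT and HT. It names no pre/post factor, baseline covariate or change from the same day's baseline. In the effect-size text, baseline means the control condition: "Effect sizes were calculated as mean change from baseline (control) to post-intervention". Change is mentioned once in connection with an analysis, in an optional secondary comparison of men and women, and its reference value is not defined.

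The documents do not say when post-treatment HRV and FMD are taken.

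**The concern.** A repeated measures analysis removes stable differences between people. It does not remove differences in one person's state from one day to another, and the study days are at least 5 days apart. The pre-treatment SDNN and % dilation are direct measures of that day's state on the outcome scale, and they are already scheduled. If the ANOVA is run on post-treatment values alone, that information is unused.

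The contrast with most at stake is Ex+HT versus Ex. Statistical Design and Power opens by asking whether heat can add to what exercise does. Yet the stated effect sizes describe combined treatment against no intervention, and no effect size or power is given for heat added to exercise. Precision for that contrast should not be given up without a reason.

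Because the outcome is undefined, the choice between post-value, change score and adjusted analysis also stays open until the data have been seen. The three can differ a good deal in precision.

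**Working it through.** **Inputs from the documents** (Statistical Design and Power)
- Two-sided α = 0.05: "Significance for each test will be evaluated with a two-sided alpha". Power 80%.
- d = 1.03 for SDNN and 1.12 for FMD, for combined treatment against control.
- The standard deviation behind d: "estimated the standard deviation from the baseline data in our pilot participants or published values".
- Stated minimum for Aim 2: "a minimum of 10 participants is required to see differences in HRV between treatments". The minimum for Aim 3 is also 10. Planned recruitment is 20 (10 men, 10 women).

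**Input assumed.** r is the correlation, within a person and across days, between the pre- and post-treatment values. It is not in the documents, so a range is shown. Equal within-person variance before and after treatment is also assumed.

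**Step 1: the plan's own figure.** Treat d as the standardized paired difference in a two-sided paired t-test (noncentral t). With d on the baseline SD, the paired value is d/√(2(1 − ρ)), which equals d only if the between-day correlation ρ is 0.5.
- SDNN, d = 1.03: power is 77% at N = 9 and 82.5% at N = 10, so the minimum is 10, as stated.
- FMD, d = 1.12: power is 78% at N = 8 and 84% at N = 9, so the minimum is 9 against the stated 10 (88.2% at 10).
- At N = 20, power is 99.2% for SDNN and 99.7% for FMD.

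The stated sizes therefore reproduce, exactly or within one, without any same-day adjustment.

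**Step 2: effect of using the pre-value.** Consider 20 participants and three active days, with the contrast variance of the post-only analysis set to 1.
- Change score: ratio = 2(1 − r).
- Covariate adjustment: ratio = (1 − r²) × (1 + 1/(f − 2)), where f is the residual degrees of freedom before the covariate enters. Here f = (20 − 1)(3 − 1) = 38, so the factor is 37/36 = 1.028. This is the cost of estimating the slope.

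| Assumed r | Adjusted, formula | Adjusted, simulated | Change score, formula | Change score, simulated |
|---|---|---|---|---|
| 0 | 1.03 | 1.03 | 2.0 | 2.01 |
| 0.3 | 0.94 | 0.94 | 1.4 | 1.42 |
| 0.5 | 0.77 | 0.76 | 1.0 | 0.98 |
| 0.7 | 0.52 | 0.51 | 0.6 | 0.58 |

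The simulation used 4,000 replicates and agrees with the formulas within simulation error. Adding period terms (up to three more degrees of freedom, f = 35) changes the factor to 34/33 = 1.030, so the loss at r = 0 remains about 3%.

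**Step 3: what this could mean for Ex+HT versus Ex.** The documents give no effect for this contrast. Purely as an illustration, assume a standardized paired difference of 0.5. Power at N = 20 is 57% unadjusted. With adjustment the standardized difference becomes 0.5/√ratio:
- r = 0: 0.5/√1.028 = 0.493, power 55%
- r = 0.3: 0.5/√0.935 = 0.517, power 59%
- r = 0.5: 0.5/√0.771 = 0.569, power 68%
- r = 0.7: 0.5/√0.524 = 0.691, power 83%

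**The case against.** The strongest reply is that the plan is silent and has not chosen a post-only analysis. A reader might infer that it discards the pre-treatment values. The documents do not support that. The dependent variable is never defined, the effect-size text and the secondary sex comparison both speak of change, and the equating of baseline with control occurs in the effect-size calculation and not in the model. It is also untrue for Control, whose SDNN and FMD value can only be a pre-treatment one. This part of the reply stands: what can be said is that the outcome is undefined and no same-day term is named.

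A reader might also infer that a poor day on Ex+HT would be counted as a treatment effect. Under randomized, counterbalanced order such variation is random error, already in the residual against which the ANOVA tests. It neither biases the contrasts nor inflates the type I error. This stands too.

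Three practical objections remain.
- Afternoon testing (stated for the first study day), supine rest and paced breathing already remove some variation, and % dilation has its own resting diameter within each scan. They may lower r, but they do not replace a pre-treatment SDNN or % dilation.
- A conventional repeated measures ANOVA does not take a covariate that changes from day to day, so a linear mixed model is needed. The plan mentions a mixed model only as an optional secondary analysis.
- Adjusting the active days leaves the Control contrast, the one behind the stated effect sizes, unresolved.

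The last two are correct and add to the work. Neither is a reason against adjusting the comparisons among Ex, HT and Ex+HT.

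**Conclusion.** The point holds as a gap in specification and a likely loss of precision, limited to SDNN and % dilation and to the contrasts among the three active conditions. If post-treatment values are analysed alone, the contrast variance is higher than it need be by an amount that depends on r. Adjustment would change it from about 3% worse at r = 0 to about 49% better at r = 0.7. At r = 0.3 the gain is small: the standard error falls by about 3% (√0.94 = 0.97). The size cannot be fixed more closely because the documents give no r.

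A reader might infer that the trial is too small. The documents do not show that. The stated minima reproduce, 20 participants are planned, and power at the stated effects is about 99% or more on the paired reading. Those effects concern combined treatment against control. For Ex+HT versus Ex no target is stated, so none can be said to be missed.

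The change is still worth making: the pre-values are already scheduled, the downside is about 3%, and the contrast that gains is the one that bears on whether heat adds to exercise.

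**What to change.** In the analysis text, for SDNN and % dilation:
- Define the outcome as the post-treatment value on each active day, and state when it is measured.
- Compare Ex, HT and Ex+HT with a linear mixed model: participant as a random or block effect, condition and period as fixed effects, and that day's pre-treatment value as a covariate, entered as its deviation from the person's mean. Add the person's mean pre-value as a second term if participants are random; it is redundant if they are fixed blocks.
- Do not use raw change scores as the primary outcome.
- Report unadjusted means alongside.
- State separately how the Control value enters. That day has only a pre-treatment measure, so it lies outside this adjustment.

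**Cost.** A few sentences of analysis text, a mixed model in place of the conventional ANOVA for these contrasts, and one or two degrees of freedom for the covariate terms. The pre-treatment values need no extra measurement. The post-treatment measurement must be written into the schedule if it is not already part of study practice.
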